4.1.4 Primary safety hypothesis

The use of PCLC to maintain hemoglobin oxygen saturation (SpO_2) level at or above 88%, as measured by the relative duration, is not inferior to the manual control (MC).

4.2 Secondary Objectives

Four additional safety related question will be addressed:

1. The rate of serious adverse events related to the PCLC is not different than those attributed to the MC group
2. The rate of serious adverse events not related to the PCLC is not different than those attributed to the MC group
3. The number of missed diagnosis attributed to the PCLC is not different than those attributed to the MC group
4. The rate of device related adverse events related to the PCLC is not different than those attributed to the MC group.

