5.2 Sample size

The target sample size is 105 subjects per study arm for a total of 210 subjects. The detail of the sample size estimation is given in section 12.

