5.6 Treatment Assignment Procedures

5.6.1 Randomization Procedures

Once informed consent has been obtained from the patient's family or legal representative, the patient will be enrolled in the study and randomly assigned to one of the two ventilatory strategies. Subjects will be randomized using a stratified, blocked randomization scheme with random block sizes of 4 and 6, generated by the study statistician. Study participants will be allocated with equal probability to each study group with stratification by center. The randomization procedure will generate a study number for each participant that links the corresponding group allocation in accordance with block size and strata. An independent statistician which is not part of the research team will validate and generate the final randomization assignment. As each subject is entered into the study, study personnel in Cincinnati will consult this randomization scheme to determine which study arms will the subject need to be assigned to.

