9.1 Specification of Safety Parameters

9.1.1 Primary Safety variable:

To assess the relative duration of time with SpO₂ <88% during the study period.

9.1.2 Secondary safety variables:

- Evaluation of missed diagnoses
- Rate of serious device-related AEs
- Rate of serious AEs not related to the device
- Rate of device-related AEs

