
For the analysis of secondary safety outcome, data point estimates will be reported with 95% confidence intervals followed by a Fisher's Exact Test at the 5% level of confidence. Specifically the percentage of subjects reporting at least one adverse event (i.e serious, any device related, etc.) will be calculated for each group and compared using Fisher's Exact Test. The relative risk of each adverse event with the corresponding two-sided 95% confidence interval will be presented.

Missing data: The primary analysis is an intent to treat analysis. In order to minimize the possibility of missing data, the total duration of monitoring will be extended for each subject as needed in order to collect at least 12 hours of evaluable data. As a sensitivity analysis, the primary outcome measure also will be calculated as the relative time the subject was on target compared to the total amount of time they were on manual or closed-loop control. Therefore each subject should have the outcome measurement. The amount of missing data is expected

to be low based on past experience with subject retention. However there is a very low probability that some subjects may die before completing 12 hours of monitoring on the device. In this case, the relative duration will be derived by using the total duration of time the subject was on target relative to the monitoring time until they died. If a subject does not have 12 hours of monitoring data on the device due to a reason other than death, we will conduct sensitivity analysis by assuming different scenarios. In a worst case scenario, the primary outcome will be computed as the total time in the target range divided by 720 minutes. In a best case scenario, the primary outcome will be computed as the total time in the target range divided by the total amount of time the subject was observed (i.e. <720 minutes). In the event of missing data on the primary safety and efficacy outcomes (except where the subject died), the reason for the missing values will be explored, and the pattern of missing values (e.g. missing at random, missing completely at random) will be evaluated. In addition, analyses excluding those subjects without 12 hours of monitoring will also be conducted as sensitivity analyses.

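### The secondary safety aims claim no difference, but their only hypothesis test is a Fisher test of difference with no margin, assumed rates or power; a non-significant result cannot support them

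*Combined protocol and SAP*

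**What the plan says.** Section 4.2 lists four safety questions: serious adverse events related to the PCLC, serious events not related to it, missed diagnoses, and device-related adverse events. Each is worded as a claim that the PCLC result does not differ from the MC result. The first reads: "The rate of serious adverse events related to the PCLC is not different than those attributed to the MC group".

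Section 9.1.2 lists the matching variables in different terms, for example "Rate of serious device-related AEs", with no mention of the PCLC.

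For the analysis, section 12.2 says that "data point estimates will be reported with 95% confidence intervals followed by a Fisher's Exact Test at the 5% level of confidence". The measure is a per-group proportion: "Specifically the percentage of subjects reporting at least one adverse event". It adds: "The relative risk of each adverse event with the corresponding two-sided 95% confidence interval will be presented".

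On size, section 5.2 states: "The target sample size is 105 subjects per study arm for a total of 210 subjects". Section 12.1 derives this from the primary efficacy endpoint and then checks it against the primary safety endpoint. Neither section 12.1 nor section 12.2 gives a margin, an assumed rate or a power for the four secondary aims.

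**The concern.** A test of difference can give evidence that two rates differ. When it is not significant, it does not show that they are the same, least of all for uncommon events in a trial sized for something else. Here the aim is a no-difference claim and the only hypothesis test offered for it is a test of difference. No text says how the aim is to be concluded.

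The plan handles the primary safety endpoint properly: a margin of 0.004, a one-sided 2.5% level and stated power in section 12.1.2, and a confidence limit compared with the margin in section 12.2. The adverse-event aims make a similar kind of claim without any of this.

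The numerator is also unsettled. Section 4.2 speaks of events related or attributed to the PCLC, section 9.1.2 of device-related events, and section 9.6.1 of relationship to the study intervention. These can give different counts in the MC arm. At stake is whether the trial's adverse-event statements say what its data can support.

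**Working it through.** **1. Where the sample size comes from (section 12.1.1).** Inputs: margin 0.12, SDs 0.33 (MC) and 0.23 (PCLC), one-sided 2.5%, power 80%, true difference 0.

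n per arm = (0.33² + 0.23²)(1.960 + 0.842)² / 0.12² = 0.1618 × 7.849 / 0.0144 = 88.2, so 89 by the normal approximation and 90 by the t distribution. The plan states 91, which is close enough. Then 91 × 1.15 = 104.65, so 105. No adverse-event rate enters this calculation.

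**2. Power of the Fisher test at that size.** Allocation is 1:1 (section 5.6.1: "Study participants will be allocated with equal probability to each study group with stratification by center"). The plan does not give the sidedness of the Fisher test, so I take it as two-sided. For MC rate p₁ and PCLC rate p₂, power is the sum of Bin(x₁; n, p₁) × Bin(x₂; n, p₂) over all pairs (x₁, x₂) with Fisher p ≤ 0.05, by full enumeration. **All rates below are assumptions.**

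| MC vs PCLC | Power, 105 per arm | Power, 91 per arm |
|---|---|---|
| 1% vs 2% | 0.7% | 0.4% |
| 1% vs 3% | 3.9% | 2.5% |
| 2% vs 4% | 4.8% | 3.5% |
| 2% vs 6% | 18.7% | 14.3% |
| 5% vs 10% | 20.2% | 16.8% |
| 1% vs 5% | 21.5% | 15.6% |
| 10% vs 20% | 45.6% | 39.8% |
| 5% vs 15% | 61.4% | 53.3% |
| 20% vs 40% | 86.3% | 80.8% |

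The 105 column is the relevant one, since section 12.2 keeps everyone who was randomized and started the assigned strategy; 91 is a lower sensitivity case. On a grid of 0.5 percentage points, the smallest PCLC rate with 80% power at 105 per arm is 7.5% against 0%, 10.5% against 1%, 18% against 5%, and 25.5% against 10%. By the usual two-proportion formula, 80% power for 5% vs 10% needs 435 per arm, and for 10% vs 20% it needs 199.

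**3. No MC events.** For x events in PCLC and none in MC, two-sided p = 2 × C(105, x) / C(210, x).
- x = 5: p = 0.0595.
- x = 6: p = 0.029.

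So at least 6 of 105 (5.7%) are needed.

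**4. What the planned relative risk would show.** Interval: exp[ln RR ± 1.96 √(1/a − 1/n + 1/b − 1/n)].
- 5 vs 5 events: RR 1.0, 95% CI 0.30 to 3.35.
- 5 vs 10 events: SE = √(0.200 + 0.100 − 0.019) = 0.530; RR 2.0, 95% CI 0.71 to 5.65. The risk difference is 4.8 percentage points, Wald 95% CI −2.2 to 11.7.

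Equal counts therefore still leave a tripling of risk inside the interval.

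**5. Where the relative risk fails.** It is undefined when MC has no events. That has probability (1 − p₁)¹⁰⁵: 0.99¹⁰⁵ = 0.35 at an assumed 1%, 0.98¹⁰⁵ = 0.12 at 2%, and 0.95¹⁰⁵ = 0.005 at 5%. An exact upper limit for a single arm still exists: for 0 of 105 it is 1 − 0.025^(1/105) = 3.5%.

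**The case against.** The strongest reply is that the plan already does most of what is needed. Section 12.2 puts estimates with 95% confidence intervals before the Fisher test and adds relative risks with intervals, so an imprecise result would be visible. No rule says that p > 0.05 establishes no difference. Section 1 rests study success only on the two primary endpoints, the primary safety endpoint has its own margin and power, and the DSMB and medical monitor oversee adverse events separately (sections 9.6.4 and 10.1). All of that stands. It rules out two readings that a reader might infer: that the Fisher test is the only basis for judgement, and that a real excess would normally be reported as no difference.

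A reader might also infer that the plan has about 20% power for these aims. It has no such figure. The 20% belongs to an assumed 5% vs 10%, and the table runs from under 1% to 86%. The documents' only cues are sparse: very few adverse events related to patient condition in the feasibility study (section 3.3), and one serious event among 95 patients in the earlier crossover trial (section 3.2.2). That trial used 4-hour periods, so it is not a planning rate.

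Finally, a reader might infer that the MC count is zero by construction because MC subjects receive no PCLC. The documents do not support this. Section 4.2 names events attributed to the MC group as the comparator, section 9.1.2 uses device-related terms, section 4.3 has MC subjects on the study ventilator too, and section 7.1.2 treats manual and automated control alike as the intervention. Section 3.3 refers to Appendix A for relatedness definitions, which the public text does not show.

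The reply leaves three gaps. The stated aim is still one that the test cannot support. The planned relative risk has no value with no MC events, and no risk difference is named. The relatedness wording still differs between sections 4.2 and 9.1.2.

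**Conclusion.** The point holds as a mismatch between aim and method. Section 4.2 claims no difference; section 12.2 offers a test of difference with no margin, rate or power, at a size set by the SpO2 endpoints. For a doubling of risk from a base of 10% or less, power at 105 per arm is below 50%, and far below it for uncommon events, so a non-significant result would be the more likely outcome even if the excess were real. For common events with a large excess, such as 20% vs 40%, power is adequate. These figures rest on assumed rates and a two-sided test.

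This does not affect the primary endpoints or study success. It affects what may be said about adverse events, and it is worth correcting because the correction is cheap.

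**What to change.** - **Section 4.2:** reword the four aims as estimation of the difference between arms.
- **Section 12.2:** add the risk difference with a 95% confidence interval, preferably by a score method given the expected counts, and an exact upper bound per arm for zero or sparse cells. Make the upper confidence limit the reported conclusion, that is, the largest excess the data do not exclude. Keep Fisher's p descriptive, state its sidedness, and say that p > 0.05 will not be read as no difference.
- **Sections 4.2 and 9.1.2:** align objectives 1, 3 and 4 with the variables, so that relatedness to the study ventilator or to the assigned FiO2 control strategy is assessed in the same way in both arms.

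A short table of detectable excess under assumed rates, as above, would set expectations. If the sponsor wants a formal conclusion instead, it must set a margin and compare the upper limit with it.

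The cost is wording and a few lines of analysis; no extra subjects or data are needed. The downside is losing the no-difference claim on these aims, which this trial could not support.

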4.3 Study Design

- The trial will employ a two group parallel design in which subjects will be randomized to one of the two ventilatory strategies for a 12 hour period. Twelve hours was selected because it captures most scenarios where mechanical ventilation could be required in the prehospital and transport environments in both military and civilian use. The two ventilatory strategies are: 1) manual adjustment of the ventilator FiO₂ by the treatment team based on physician order or according to current protocol (manual control period) or 2) automatic adjustment by the system algorithm (closed-loop period). Manual adjustment will use the same SpO₂ target (94%) as the closed loop system. During closed-loop control, the FiO₂ can be overridden by the clinician at any time.
- This is a multicenter trial with four sites (The University of Cincinnati Level 1 Trauma Center, The Los Angeles County Medical Center Level 1 Trauma Center, The University of Texas Health Science Center at Houston Level 1 Trauma Center, and Regions Hospital Level 1 Trauma Center). All patients age 18 to 65 inclusive admitted to the Trauma/Acute Care service and requiring invasive mechanical ventilation will be screened for the study. This age range is intended to represent the group of warfighters and support personnel to be treated with this system. These patients will be unable to provide consent due to the severity of their injuries. Their legal representative will be approached as soon as possible. Once consent has been obtained the patient will be randomly assigned to one of the two study arms and enrolled in the study; subjects are not considered to be enrolled in the study until they have been successfully randomized to receive either CLC or manual control of the study ventilator.
- Baseline characteristics including demographic information, anatomic Injury Severity Score (ISS), physical exam findings, and physiologic (APACHE II) markers of disease severity, and admitting diagnoses will be assessed for all subjects. An arterial blood gas obtained prior to study enrollment will be recorded to define the degree of lung injury. Ventilator settings and vital signs immediately prior to the start of the clinical study will also be recorded.

Subjects will be studied for a total of 12 hours and will be monitored for an additional 24 hours

- During the entire study period, oxyhemoglobin saturation (SpO₂) will be continuously recorded. In addition, patient vital signs and ventilator settings (mode, respiratory rate, tidal volume, FiO₂, airway pressures, PEEP) will be monitored continuously and recorded. Any blood gases (including pH, PaCO₂, and PaO₂) performed for routine care will also be recorded. Following the first hour of each study period, a single blood gas will be drawn to verify the relationship of SpO₂ and SaO₂ and to assure adequate PaCO₂ and pH. The total amount of blood drawn will be ~1 teaspoon (5 ml). During each study period the number of manipulations of FiO₂ by clinicians and by the system algorithm will be recorded automatically. The Case Report Form will also capture the times of any clinically significant events (hypotension, defibrillation, adjustment of FiO₂ by ≥10%) and these times will be merged to the measurement times. This data acquisition plan (collection of data from the monitor, ventilator, and CRF elements) will provide the ability to interpret the results in detail and monitor the safety of the trial.

As noted previously, the primary efficacy variable will be control of SpO₂ within the target range, 92 to 96%. The table below compares the protocol for both the manual and PCLC periods.

Variable	Manual Control	Closed-Loop Control
FiO ₂	Set as directed by clinician	Set as directed by clinician
SpO ₂ Target	92 to 96% following the Manual Protocol, Figure 3	92 to 96%, using the PCLC system
SpO ₂ Desaturation Upper Limit	88%	88%
If Desaturation Occurs	Follow manual control protocol (figure 3)	Permit closed-loop algorithm to manage unless otherwise directed by clinician.

When the subject is in the manual control period, FiO₂ will be adjusted manually following the protocol in Figure 3. If SpO₂ falls below 88%, the ventilator will trigger the Low SpO₂ alarm (medium priority) and the treatment team will respond and take corrective actions. This is the current standard of care. In order for this to take place, the alarm must trigger, a caregiver must respond, determine the cause, and take corrective action.

[figure not shown]

Figure 3

The closed-loop control system includes both audible and visual alarms to alert the clinician of an unreliable signal from the pulse oximeter, malposition of the pulse oximeter sensor, and subject SpO₂ less than 88%. Details of these alarms are documented in Appendix B which is taken from the Operation Manual. All alarms and low SpO₂ conditions will be recorded automatically on the laptop computer data logger.

If the subject requires a procedure in the ICU that the standard of care requires an increase in FiO₂ to 1.0 (e.g. bronchoscopy) the data collection will automatically continue but such data will

not be considered in the statistical analysis because such procedures are not part of the trial protocol. The Case Report Form will capture such events and note the times that such procedures began and were completed. Data inclusion in the statistical analysis will resume once FiO₂ control returns to the trial protocol. If the subject requires transfer to the operating room, radiology for treatment or some other non-ICU location, data collection will not be included in the statistical analysis until the subject returns to the ICU. These incidents outside of the ICU will also be captured on the Case Report Form. The goal of the study will be to have a minimum of 12 hours of data collection for each subject in either arm of the study

5. STUDY ENROLLMENT AND WITHDRAWAL

5.1 Study population

All patients between the ages of 18 and 65 inclusive, admitted to the Trauma/Acute Care service and requiring invasive mechanical ventilation will be screened for the study. This age range is intended to represent the group of warfighters and support personnel to be treated with this system.

5.2 Sample size

The target sample size is 105 subjects per study arm for a total of 210 subjects. The detail of the sample size estimation is given in section 12.

5.3 Subject Inclusion Criteria

All subjects must meet all of the inclusion criteria and none of the exclusion criteria in order to be eligible to participate:

- The subject's legally authorized representative will provide signed and dated informed consent.
- Age 18 - 65, inclusive.
- Admission to a surgical or neurosurgical intensive care unit following traumatic injury or acute surgical illness
- Requirement for endotracheal intubation
- Requirement for mechanical ventilation
- Patient is currently receiving inspired oxygen concentration (FiO₂) ≥40%

5.4 Subject Exclusion Criteria

An individual who meets any of the following criteria will be excluded from participation in this study:

- Age under 18 or over 65
- Isolated or severe head injury (Glasgow Coma Scale = 6 or less) with expected survival less than 24 hours
- Brain death
- Anticipated survival less than 48 hours

- Pregnant female
- Patient in whom a pulse oximeter cannot detect a reliable signal due to hypotension, hypothermia, or other injury
- Known carbon monoxide poisoning
- Uncontrolled diabetic
- Patient who is unable to maintain SpO₂ level of 88% at an FiO₂ of 100% due to their medical condition.

(NOTE: Being in the trial would impose no additional risk to a patient who presents with this condition however, data from a patient presenting with this pathophysiology would not provide insight into the performance of the controller as it would simply maintain that patient on an FiO₂ of 100%.)

- Patient with chronic hypercarbia.
- Patient where a physician believes that FiO₂ PCLC could be detrimental to the management of the patient.
- Prisoner
- SpO₂ to SaO₂ difference >4%
- Patient with core temperature <35° C

5.5 Strategies for Recruitment and Retention

There will be no compensation to subjects for study participation.

We anticipate subject participation not to exceed 24 hours of data collection (to produce 12 hours of evaluable data) for the entire study; however subjects will be monitored for adverse events for 24 hours following the end of the intervention. Subjects will be terminated from the study after the 24 hour period ends.

We have chosen the four Level 1 trauma units to maximize recruitment of a study population that meets all of the inclusion criteria. Each trauma unit admits approximately 85 trauma patients/year that would be eligible for this study and we plan to recruit equal numbers of subjects from each trauma unit. If this is not feasible, no more than 60% of the total subjects will come from a single study site.

5.6 Treatment Assignment Procedures

5.6.1 Randomization Procedures

Once informed consent has been obtained from the patient's family or legal representative, the patient will be enrolled in the study and randomly assigned to one of the two ventilatory strategies. Subjects will be randomized using a stratified, blocked randomization scheme with random block sizes of 4 and 6, generated by the study statistician. Study participants will be allocated with equal probability to each study group with stratification by center. The randomization procedure will generate a study number for each participant that links the corresponding group allocation in accordance with block size and strata. An independent statistician which is not part of the research team will validate and generate the final randomization assignment. As each subject is entered into the study, study personnel in Cincinnati will consult this randomization scheme to determine which study arms will the subject need to be assigned to.

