8.2 Clinical Laboratory Evaluations

1. Baseline blood gas analyses, as ordered by the clinical team.
2. Arterial blood gases
3. Continuous transcutaneous oxygen saturation

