12. STATISTICAL CONSIDERATIONS

12.1 Sample size

12.1.1 Primary Efficacy objective:

The primary efficacy endpoint is the relative duration of time where SpO₂ remains between 92 and 96% (inclusive). This will be obtained from continuously monitoring the subjects SpO₂ level throughout the study period such that at least 12 hours of monitoring data are available for each subject. The difference in the average amount of time will be the basis for the efficacy outcome comparison between the two ventilatory strategies.

To assess power for this objective the sample size calculation is based on preliminary data estimating the relative duration of time that SpO₂ remains between 92 and 96% (inclusive). To determine the noninferiority margin, the guidelines provided by FDA were followed (<http://www.fda.gov/downloads/drugs/guidancecomplianceregulatoryinformation/guidances/ucm202140.pdf>). From our preliminary data, the relative duration of time in which the SpO₂ remained between 92 and 96% in a four hour time interval for the MC group was 0.30 with 95% CI (0.23, 0.38). Following the guideline mentioned above we used half of the lower confidence bound to be the margin of non-inferiority (i.e. 0.12, which is equivalent to 7.2 minutes per hour) From our preliminary data, the SD for the MC and PCLC group was 0.33 and 0.23 respectively. Assuming a noninferiority margin of 0.12, a sample size of 91 subjects per group will achieve 80% power with a 2.5% one-sided significant level when the true difference between the group means is assumed to be zero. Allowing a 15% attrition rate for potential withdrawal of subjects the required sample size is 105 per group.

12.1.2 Primary Safety objective:

The primary safety endpoint is the relative duration of time with SpO₂ <88% over the study period. This will be observed by continuously monitoring each subject's SpO₂ level throughout the study period such that at least 12 hours of monitoring data are available for each subject. From our preliminary data the observed relative time where SpO₂ <88% was 0.004 and 0.002 for the MC and PCLC group respectively. The proposed sample size of 105 per group will allow us to conclude non-inferiority with a margin of 0.004 (which is equivalent to 15 seconds/hr) with 95% power with a 2.5% one-sided significant level.

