12.2 Statistical Analysis

For the primary outcomes, the intent-to-treat (ITT) population will be used for all efficacy and safety analyses. All subjects that were randomized and started the assigned ventilation strategy protocol will be included in the ITT. All summary tables for quantitative parameters will display mean, standard deviation, median, interquartile range, and range (minimum and maximum), as well as number of missing data (if relevant). All summary tables for qualitative parameters will display counts, percentages and number of missing data if relevant. Baseline characteristics will be described using the ITT population. Demographics, medical history and other baseline variables will be summarized as appropriate to the type of data. The primary effectiveness outcome will be defined as the proportion of time during the 12 hour monitoring period that the subject's SpO₂ levels were within the target range relative to the actual total monitoring time (which is targeted to be 12 hours for all subjects). By using the proportion of time instead of the actual time, we are able to normalize the outcome based on the total amount of monitoring time available. We will assess normality of the response variables within each of the two groups by visual inspection of the histograms and box plots and by performing the test for normality of data using the Shapiro Wilk test. If the assumption of normality for the primary effectiveness outcome does not seem tenable, we will use the arcsine square root transformation which is recommended to normalize skewed percentage data. A one-sided lower 97.5% confidence interval will be calculated for the difference between the two monitoring strategy groups (PCLC minus MC) in terms of the effectiveness outcome (duration where SpO₂ remains between 92 and 96% relative to the total monitoring time) and the lower limit will be compared to the noninferiority margin of 0.12. Similar analyses will be conducted for the secondary effectiveness outcome with the only difference being the way the duration is calculated for the secondary effectiveness outcome. For this analysis, the target duration will be calculated as amount of time that SpO₂ remains between 92 and 96% when FiO₂ > 21% and SpO₂ ≥ 92% when FiO₂ = 21%. The safety outcome (duration where SpO₂ remains above 88% relative to the total monitoring time) will be assessed using a one-sided lower 97.5% confidence interval and the lower limit will be compared to the non-inferiority margin of 0.004. If non-inferiority is established for an endpoint, we will proceed in conducting a superiority test and will compare the lower confidence limit to 0.

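### The primary effectiveness limit ignores the randomisation stratum (center) and the recorded baseline FiO2, which may give up some precision; the planned analysis is still valid

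*Combined protocol and SAP*

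**What the plan says.** Section 5.6.1 describes blocked randomisation (block sizes 4 and 6) at four centers: "Study participants will be allocated with equal probability to each study group with stratification by center".

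Section 12.2 sets out the effectiveness test: "A one-sided lower 97.5% confidence interval will be calculated for the difference between the two monitoring strategy groups (PCLC minus MC"). The lower limit is compared with the margin of 0.12. Neither center nor any covariate is named. If normality looks untenable, an arcsine square-root transformation is to be used. The stated role of baseline data is descriptive: "Baseline characteristics will be described using the ITT population".

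Baseline FiO2 should be available for every subject. Section 4.3 says: "Ventilator settings and vital signs immediately prior to the start of the clinical study will also be recorded", and elsewhere in that section FiO2 is listed as one of the ventilator settings. Eligibility (section 5.3) also depends on it: "Patient is currently receiving inspired oxygen concentration" of at least 40%.

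Baseline blood gases are less certain. Section 4.3 says a pre-enrolment gas will be recorded, but section 8.2 lists "Baseline blood gas analyses, as ordered by the clinical team".

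**The concern.** When randomisation is stratified on a factor that predicts the outcome, the stratification removes between-center imbalance from the estimated difference. A plain two-sample standard error does not credit this, so the limit is wider than it needs to be. Leaving out a prognostic baseline variable has a similar cost: it does not bias a randomised comparison, but variance that could be explained stays in the error term.

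Study success requires non-inferiority on both effectiveness and safety, and effectiveness was planned at 80% power. The effectiveness decision therefore rests on one limit with a fair chance of missing the margin if the arms are truly equal. Adjustment has to be prespecified to be credible, so the choice must be made before the data are seen.

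**Working it through.** **Inputs from section 12.1.1.** Margin 0.12; true difference 0; one-sided 2.5%; 91 evaluable and 105 enrolled per group; "the SD for the MC and PCLC group was 0.33 and 0.23 respectively". The R² of center and baseline FiO2 for time in range is not in the documents, so it is an assumption and is shown as a range.

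**Reproducing the plan's figure.** n = (1.96 + 0.8416)² × (0.33² + 0.23²) / 0.12² = 7.849 × 0.1618 / 0.0144 = 88.2, so 89 per group; the Welch t version needs 90. At 91 per group, SE = sqrt(0.1618/91) = 0.0422 and power = Φ(0.12/0.0422 − 1.96) = 81.2% (80.8% by Welch t). The plan's 91 for 80% power is therefore confirmed, by a formula with no stratum or covariate.

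**Effect of explained variance.** SE = 0.0422 × sqrt(1 − R²) at 91 per group, and power = Φ(0.12/SE − 1.96):

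| Assumed R² | SE (91/group) | Estimate to limit | Power, 91/group | Power, 105/group | n/group for 80% |
|---|---|---|---|---|---|
| 0 | 0.0422 | 0.0826 | 81.2% | 86.4% | 89 |
| 0.05 | 0.0411 | 0.0806 | 83.1% | 88.0% | 84 |
| 0.10 | 0.0400 | 0.0784 | 85.1% | 89.7% | 80 |
| 0.20 | 0.0377 | 0.0739 | 88.9% | 92.8% | 71 |
| 0.30 | 0.0353 | 0.0691 | 92.5% | 95.5% | 62 |

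The formula assumes equal proportional gain in both arms and charges nothing for estimating the extra terms, so the model was also simulated.

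**Simulation of the proposed model.** 182 subjects, four near-equal centers, blocks of 4 and 6, normal residuals, baseline FiO2 with a floor of 0.40, 4,000 runs per scenario. The unadjusted Welch limit is compared with a linear model using HC3 standard errors.

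| Scenario (share of variance explained) | Unadjusted power | Adjusted power | Change (points) |
|---|---|---|---|
| Nothing predictive | 81.3% | 80.3% | −1.0 |
| Center 10%, both arms; center term only | 81.7% | 83.9% | +2.2 |
| Center 10%, MC only; center term only | 82.4% | 82.6% | +0.2 |
| Center 2%, FiO2 5%, both arms | 80.2% | 81.7% | +1.5 |
| Center 2%, FiO2 10%, both arms | 80.8% | 84.0% | +3.2 |
| Center 2%, FiO2 20%, both arms | 79.9% | 88.3% | +8.4 |
| FiO2 10%, MC only | 81.1% | 82.0% | +0.9 |
| FiO2 20%, MC only | 79.6% | 82.6% | +3.0 |

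With 60% of subjects at one site, the most that section 5.5 allows, and center 2% and FiO2 10%, power went from 80.5% to 83.6%, so the near-equal-center assumption is not critical.

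**Type I error at a true difference of −0.12.** Averaged over the simulated scenarios it was 2.6% unadjusted and 2.5% adjusted. In a separate simulation with larger center effects, the unadjusted limit became conservative: 2.5% with nothing predictive, 2.0% with center and FiO2 each explaining 5% or each 10%, and 1.6% with center 20% and FiO2 10%. In that last case an adjusted model with a less conservative robust standard error than HC3 reached 3.1%. Further HC3 runs gave 2.1% to 2.8% in every scenario, which is why HC3 is specified.

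**Safety endpoint.** The SDs of desaturation time in the earlier four-hour crossover trial (section 3.2.2) give 2.64/240 = 0.0110 and 1.37/240 = 0.0057. At 91 per group SE = 0.0013. Power is Φ(0.004/0.0013 − 1.96) = 86.8% at zero difference and Φ(0.006/0.0013 − 1.96) = 99.6% at the planning difference of 0.002. There is little to gain.

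**The case against.** The strongest reply is that nothing here is wrong. The unadjusted limit is valid, the sample size reproduces, and the plan is silent on adjustment rather than ruling it out. That stands, and it is why this is only a suggestion.

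Second, the benefit is assumed. The controller resets FiO2 throughout the 12 hours, so the starting value may matter little in the PCLC arm; the MC-only rows, with gains of 0.2 to 3.0 points, may be nearer the truth than the +8. The relationship may also not be linear: subjects on low FiO2 may sit above 96% and those on high FiO2 below 92%, and a linear term could then explain little. Both points stand. Against them, section 3.2.2 reports that time in range in the first animal study rose from 64% to 73% when periods with FiO2 at its extremes were excluded. The secondary effectiveness endpoint also treats FiO2 of 21% separately. These suggest that oxygen need matters, but not how much.

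Third, 91 per group is the less favourable baseline. If all 105 per group contribute, unadjusted power is already 86.4%. With an assumed true advantage of 0.05 at 91 per group it is Φ(0.17/0.0422 − 1.96), about 98%. That stands, and narrows the room for gain.

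Fourth, the simulation uses normal residuals, whereas a proportion with mean 0.30 and SD 0.33 is bounded and skewed: a normal curve with those values puts Φ(−0.30/0.33), about 18%, below zero. The simulated gains are therefore approximate.

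Fifth, working on the original scale displaces the conditional arcsine step. This is a real change and should be stated openly. The 0.12 margin is itself defined on the proportion scale, so the change is consistent with it.

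**Conclusion.** The point holds as an efficiency matter. The analysis omits the factor used to stratify randomisation and a baseline value that the trial already records. That the value is recorded is inferred from two statements in section 4.3 and the entry criterion, read together.

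The expected effect of adjusting is between about −1 and +8 points of effectiveness power at 91 per group. The upper end needs baseline FiO2 to explain about 20% of the variance in both arms. Center alone probably contributes little, because both arms share one SpO2 target and FiO2 in the manual arm "will be adjusted manually following the protocol in Figure 3". Most of any gain would come from FiO2.

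These sizes rest on assumed R² values, normal residuals and a true difference of zero. The trial is not underpowered without the change, and no gain is claimed for safety. Priority is low and confidence in the size is moderate.

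**What to change.** In section 12.2, define the primary effectiveness estimate as the PCLC-minus-MC difference from a linear model on the original proportion scale. Include arm, center (four levels) and one prespecified covariate: the FiO2 setting recorded immediately before study start. Use HC3 standard errors, because the planning SDs differ between arms. Compare the one-sided 97.5% lower limit with the unchanged margin, and report the unadjusted difference as a sensitivity analysis. State that this model replaces the conditional arcsine transformation for the primary limit.

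Do not add PaO2/FiO2 unless the pre-enrolment blood gas is available for every subject or a rule for missing covariate values is set in advance. Leave the safety analysis unadjusted.

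The cost is one or two sentences in the SAP and about one point of power if neither term is predictive. No new data are needed, and the target difference, confidence level and margins stay the same.
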